- c. For participants who discontinue study intervention administrations, every effort should be made to conduct final efficacy and safety assessments. Participants who permanently discontinue study intervention, but do not withdraw from study participation, should be followed at all subsequent study visits through Week 60. Week 52 may serve as the final safety follow-up visit if study medication was stopped on or before Week 40, but a full physical exam should be performed at that visit (Week 52). Sites will be notified after all enrolled participants have completed the Week 20 visit or discontinued study intervention prior to Week 24. Participants who are receiving study intervention will then complete a final efficacy visit approximately 4 weeks after the last administration of study intervention and the final safety follow-up visit approximately 12 weeks after the last administration of study intervention.
 - d. Participants who discontinue study intervention administrations and do not wish to continue in the study should return 12 weeks after the last study intervention administration for a final safety follow-up visit and complete assessment as indicated for Week 60.
 - e. Chemistry, hematology, and UPCR (x2) must be completed after the participant has received at least 8 weeks of MMF/MPA.
 - f. Refer to [Table 2](#) for additional Week 52 assessments to be performed for participants who continue in the long-term extension (LTE).
 - g. These assessments will be performed for participants who complete their Week 52 visit, but do not enter the LTE.
 - h. Urinalysis assessments should not be done within 48 hours after biopsy to limit possible blood from biopsy in urine.

Table 2: Schedule of Activities – Long-term Extension for Eligible Participants (through Week 104)																	
Week	52 ^a	56	60	64	68	72	76	80	84	88	92	96	100	104	Final Efficacy Visit ^b	Final Safety Follow-up Visit ^c	Notes
Study Procedure^d																	
Visit Window	± 7 days																
Administrative																	
Informed consent	X																Confirm participant consented to participate in LTE
Provide/Collect and review participant diary card			X		X		X		X		X		X				For participant/caregiver who is administering study intervention at home. Training should be provided at Week 60 or initial dispensation.
Study Intervention Administration																	
Instruction for self administration			X														At home administration by participant/caregiver is at the investigator's and participant's discretion, and upon completion of training. Participant/caregiver will administer the first dose in the LTE at Week 60 in the presence of qualified study site staff and subsequent administrations of study intervention can be self administered by the participant/caregiver at home.
Dispense study intervention to participant/caregiver			X		X		X		X		X		X				Dispense study intervention to participant/caregiver who will administer next dose of study intervention at home.
Study intervention SC injection (at site/at home)	X	X	X	X ^e	X	X ^e	X	X ^e	X	X ^e	X	X ^e	X	X ^e			At home administration may begin with Week 64 administration of study intervention according to regional/local regulations and instructions. Participants will have option of continuing to receive injections at site by study site personnel. The PFS Y drug device (a prefilled syringe with autoinjector) will be used for at home administration. The PFS Y or PFS U could be used at site for study intervention administration by site staff depending on availability. If PFS Y is not available at site for at home administration, then administration of study intervention will occur at study site.

Table 2: Schedule of Activities – Long-term Extension for Eligible Participants (through Week 104)																	
Week	52 ^a	56	60	64	68	72	76	80	84	88	92	96	100	104	Final Efficacy Visit ^b	Final Safety Follow-up Visit ^c	Notes
Efficacy Assessments																	
PROs																	Whenever possible, PRO assessments should be conducted before any tests, procedures, or other consultations for that visit to prevent influencing participants' perceptions. It is recommended that PROs be performed in the following sequence: FACIT Fatigue, PGIC, lupus symptoms (assessment of joint pain, joint stiffness, rash, and swelling), and LupusQoL
FACIT Fatigue					X				X				X		X		
PGIC					X				X				X		X		
Lupus Symptoms					X				X				X		X		
LupusQoL					X				X				X		X		
ClinROs																	
SLEDAI 2K					X				X				X		X		
PGA of Disease Activity					X				X				X		X		
Joint Count Assessment					X				X				X		X		
Cutaneous Lupus (CLASI)					X				X				X		X		
Safety Assessments																	
Full physical examination																	X
eC SSRS			X		X		X		X		X		X		X		X
Targeted physical examination		X	X		X		X		X		X		X		X		
Vital signs		X	X		X		X		X		X		X		X		X
Weight							X						X		X		
TB evaluation		X	X		X		X		X		X		X		X	X	TB evaluation includes an assessment of recent exposure or risk of TB including new or chronic cough, fever, night sweats, unintentional weight loss or recent contact with someone with active TB. If TB is suspected at any time during the study, a chest x ray (consistent with local regulations), and QuantiFERON® TB test should be performed. A TST is additionally required if the QuantiFERON® TB test is not registered/approved locally or the

Table 2: Schedule of Activities – Long-term Extension for Eligible Participants (through Week 104)																	
Week	52 ^a	56	60	64	68	72	76	80	84	88	92	96	100	104	Final Efficacy Visit ^b	Final Safety Follow-up Visit ^c	Notes
																	TST is mandated by local health authorities.
Urine pregnancy test (β HCG)		X	X		X		X		X		X		X		X	X	Females of childbearing potential only
Review concomitant therapy		X	X		X		X		X		X		X		X	X	
Adverse events		X	X	X	X	X	X	X	X	X	X	X	X	X	X	X	Participants/caregiver who administer study intervention at home will be asked to identify signs or symptoms related to AEs before study intervention administration and will be asked to contact the study doctor before administration if a symptom is identified.
Injection site evaluation		X	X	X	X	X	X	X	X	X	X	X	X	X			Participants who receive study intervention at site should be monitored for injection site reaction post injection; duration of observation period is at investigator's discretion. Participants/caregivers who will administer study intervention at home will be trained to perform self evaluation for injection site reactions and report adverse events.
Clinical Laboratory Tests																	
Chemistry			X		X		X		X		X		X		X	X	
Cystatin C			X		X		X		X		X		X		X	X	
Hematology			X		X		X		X		X		X		X	X	
Coagulation					X				X				X		X		
Antinuclear antibodies															X		
Anti dsDNA, C3, C4					X				X				X		X	X	
Other autoantibodies					X				X				X		X	X	
Anti phospholipid antibodies					X				X				X		X	X	If an abnormal test result is not obtained at Screening or Week 0, no additional follow up testing is required. However, additional testing may be performed if clinically indicated.
Ig isotype profile					X				X				X		X	X	
Urine Analyses (spot urine)																	
Urinalysis (dipstick, all participants)			X		X		X		X		X		X		X	X	
Urine protein/creatinine ratio			X		X		X		X		X		X		X	X	Must be collected on first morning void specimens.

Week	52 ^a	56	60	64	68	72	76	80	84	88	92	96	100	104	Final Efficacy Visit ^b	Final Safety Follow-up Visit ^c	Notes
Urine sediment analysis			X		X		X		X		X		X		X		
Pharmacokinetic/Immunogenicity Assessments																	
Serum guselkumab concentrations ^f							X						X		X	X	
Antibodies to study intervention ^f							X						X		X	X	
Biomarkers (where local regulations permit)																	
Serum biomarkers													X		X		
Urine biomarkers													X		X		This sample needs to be processed as per the procedure in the laboratory manual, with centrifugation and freezing of the supernatant.
Whole blood (RNA)													X		X		
Pharmacogenomics (DNA)																	
Blood sample collection (optional)															X		
Abbreviations: ADA anti drug antibody; AE adverse events; β HCG beta human chorionic gonadotropin; CLASI Cutaneous Lupus Erythematosus Disease Area and Severity Index; ClinROs Clinical Reported Outcomes; DNA deoxyribonucleic acid; dsDNA double stranded DNA; eC SSRS electronic Columbia Suicide Severity Rating Scale; FACIT Functional Assessment of Chronic Illness Therapy; Ig immunoglobulin; LTE long term extension; LupusQoL Lupus Quality of Life; PFS U prefilled syringe with an UltraSafe Plus™ Passive Needle Guard; PFS Y prefilled syringe with Ypsomate autoinjector; PGA Physician's Global Assessment; PGIC Patient Global Impression of Change; PK pharmacokinetics; PRO patient reported outcomes; RNA ribonucleic acid; SC subcutaneous; SLEDAI 2K SLE disease activity index 2000; TB tuberculosis; TST tuberculin skin test.																	

Footnotes:

- Refer to Table 1 for additional Week 52 assessments that must be performed.
- These assessments should be performed at the time of study intervention discontinuation, at the time of study participation termination, or upon notification to sites of early study termination.
- These assessments should be performed approximately 12 weeks after a participant's last dose of study intervention (for participants who have not withdrawn consent).
- Unless otherwise specified, all assessments (except for injection site evaluation) are to be completed prior to study intervention administration.
- Study intervention may be administered at home by trained participant/caregiver.
- For visits with study intervention administration, all blood samples for assessing predose guselkumab concentration and antibodies to study intervention MUST be collected BEFORE the administration of the study intervention. When both PK/ADA samples are collected, 1 sample (instead of 2) will be collected for both assays.

Table 3: Schedule of Activities – Long-term Extension for Eligible Participants (Weeks 108 to 160)														
Week	108	112	116	120	124	128	132	136	140	144	148	152/ Final Efficacy Visit ^a	160/Final Safety Follow-up Visit ^b	Notes
Study Procedure^c														
Visit Window	± 7 days													
Administrative														
Provide/Collect and review participant diary card	X		X		X		X		X		X			For participant/caregiver who is administering study intervention at home. Training should be provided at Week 60 or initial dispensation.
Study Intervention Administration														
Dispense study intervention to participant/caregiver	X		X		X		X		X					Dispense study intervention to participant/caregiver who will administer next dose of study intervention at home.
Study intervention SC injection (at site/at home)	X	X ^d	X	X ^d	X	X ^d	X	X ^d	X	X ^d	X			At home administration may begin with Week 64 administration of study intervention according to regional/local regulations and instructions. Participants will have option of continuing to receive injections at site by study site personnel. The PFS Y drug device (a prefilled syringe with autoinjector) will be used for at home administration. The PFS Y or PFS U could be used at site for study intervention administration by site staff depending on availability. If PFS Y is not available at site for at home administration, then administration of study intervention will occur at study site.
Efficacy Assessments														
PROs														Whenever possible, patient reported outcome assessments should be conducted before any tests, procedures, or other consultations for that visit to prevent influencing participants' perceptions. It is recommended that PROs be performed in the following sequence: FACIT fatigue, PGIC, lupus symptoms (assessment of joint pain, joint stiffness, rash, and swelling), and LupusQoL
FACIT Fatigue			X				X						X	
PGIC			X				X						X	
Lupus Symptoms			X				X						X	
LupusQoL			X				X						X	
ClinROs														
SLEDAI 2K			X				X						X	
PGA of Disease Activity			X				X						X	
Joint Count Assessment			X				X						X	
Cutaneous Lupus (CLASI)			X				X						X	
Safety Assessments														
Full physical examination													X	

Table 3: Schedule of Activities – Long-term Extension for Eligible Participants (Weeks 108 to 160)														
Week	108	112	116	120	124	128	132	136	140	144	148	152/ Final Efficacy Visit ^a	160/Final Safety Follow-up Visit ^b	Notes
eC SSRS	X		X		X		X		X		X	X	X	
Targeted physical examination	X		X		X		X		X		X	X		
Vital signs	X		X		X		X		X		X	X	X	
Weight					X						X	X		
TB evaluation	X		X		X		X		X		X	X	X	TB evaluation includes an assessment of recent exposure or risk of TB including new or chronic cough, fever, night sweats, unintentional weight loss or recent contact with someone with active TB. If TB is suspected at any time during the study, a chest x ray (consistent with local regulations), and QuantiFERON [®] TB test should be performed. A TST is additionally required if the QuantiFERON [®] TB test is not registered/approved locally or the TST is mandated by local health authorities.
Urine pregnancy test (β HCG)	X		X		X		X		X		X	X	X	Females of childbearing potential only.
Review concomitant therapy	X		X		X		X		X		X	X	X	
Adverse events	X	X	X	X	X	X	X	X	X	X	X	X	X	Participants/caregiver who administer study intervention at home will be asked to identify signs or symptoms related to AEs before study intervention administration and will be asked to contact the study doctor before administration if a symptom is identified.
Injection site evaluation	X	X	X	X	X	X	X	X	X	X	X			Participants who receive study intervention at site should be monitored for injection site reaction post injection; duration of observation period is at investigator's discretion. Participants/caregivers who will administer study intervention at home will be trained to perform self evaluation for injection site reactions and report adverse events.
Clinical Laboratory Tests														
Chemistry	X		X		X		X		X			X	X	
Cystatin C	X		X		X		X		X			X	X	
Hematology	X		X		X		X		X			X	X	
Coagulation			X				X					X		
Antinuclear antibodies												X		
Anti dsDNA, C3, C4			X				X					X	X	
Other autoantibodies			X				X					X	X	
Anti phospholipid antibodies			X				X					X	X	If an abnormal test result is not obtained at Screening or Week 0, no additional follow up testing is required. However, additional testing may be performed if clinically indicated.
Ig isotype profile			X				X					X	X	
Urine Analyses (spot urine)														

Week	108	112	116	120	124	128	132	136	140	144	148	152/ Final Efficacy Visit ^a	160/Final Safety Follow-up Visit ^b	Notes
Urinalysis (dipstick, all participants)	X		X		X		X		X		X	X	X	
Urine protein/creatinine ratio	X		X		X		X		X		X	X	X	Must be collected on first morning void specimens.
Urine sediment analysis	X		X		X		X		X		X	X		
Pharmacokinetic/Immunogenicity Assessments														
Serum guselkumab concentrations ^c												X	X	
Antibodies to study intervention ^c												X	X	
Biomarkers (where local regulations permit)														
Serum biomarkers											X	X		
Urine biomarkers											X	X		This sample needs to be processed as per the procedure in the laboratory manual, with centrifugation and freezing of the supernatant.
Whole blood (RNA)											X	X		
Pharmacogenomics (DNA)														
Blood sample collection (optional)												X		
Abbreviations: ADA anti drug antibody; AE adverse events; β HCG beta human chorionic gonadotropin; CLASI Cutaneous Lupus Erythematosus Disease Area and Severity Index; ClinROs Clinical Reported Outcomes; DNA deoxyribonucleic acid; dsDNA double stranded DNA; eC SSRS electronic Columbia Suicide Severity Rating Scale; FACIT Functional Assessment of Chronic Illness Therapy; Ig immunoglobulin; LTE long term extension; LupusQoL Lupus Quality of Life; PFS U prefilled syringe with an UltraSafe Plus™ Passive Needle Guard; PFS Y prefilled syringe with YpsoMate autoinjector; PGA Physician's Global Assessment; PGIC Patient Global Impression of Change; PK pharmacokinetics; PRO patient reported outcomes; RNA ribonucleic acid; SC subcutaneous; SLEDAI 2K SLE disease activity index 2000; TB tuberculosis; TST tuberculin skin test.														

Footnotes:

- These assessments should be performed at Week 152, at the time of study intervention discontinuation, at the time of study participation termination, or upon notification to sites of early study termination.
- These assessments should be performed at Week 160 or approximately 12 weeks after a participant's last dose of study intervention for participants who have not withdrawn consent.
- Unless otherwise specified, all assessments (except for injection site evaluation) are to be completed prior to study intervention administration.
- Study intervention may be administered at home by trained participant/caregiver.
- For visits with study intervention administration, all blood samples for assessing predose guselkumab concentration and antibodies to study intervention MUST be collected BEFORE the administration of the study intervention. When both PK/ADA samples are collected, 1 sample (instead of 2) will be collected for both assays.

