Key safety assessments include AEs, clinical laboratory tests (hematology and chemistry), systolic and diastolic blood pressures over time, monitoring for hypersensitivity reactions, AEs temporally

associated with infusion, injection-site reactions, suicidality assessment, and early detection of active tuberculosis (TB).

Participants who complete the Week 52 visit and achieve a complete renal response, may have the option to participate in an LTE study; see Section 4.1.2 for further details.

Participants who experience an LN flare during the main study will be discontinued from study intervention. An LN flare is defined as an increase in proteinuria and/or serum creatinine concentration, abnormal urine sediment or a reduction in creatinine clearance rate as a result of active disease requiring a change in an immunomodulatory medication for LN beyond that which is outlined in Section 6.5.

An external, independent DMC will be commissioned for this study (Section 9.5). The DMC will review unblinded data on a periodic basis to ensure the safety of participants enrolled in the study. The main focus of the DMC will be on reviewing interim unblinded safety data, but the DMC may also review efficacy data needed to ensure the full benefit:risk profile for guselkumab. The DMC responsibilities, authorities, and procedures will be documented in a separate DMC charter.

A diagram of the study design is provided in Section 1.2, Schema.

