Has a chest radiograph (both posterior-anterior and lateral views, or per country regulations where applicable), taken within 12 weeks prior to randomization and read by a qualified radiologist (or pulmonologist in accordance with local regulations), with no evidence of current, active TB or old, inactive TB. A chest computed tomography (CT) scan is also acceptable if obtained instead of a chest radiograph outside of the protocol.

Contraception

Contraceptive (birth control) use by men or women should be consistent with local regulations regarding the acceptable methods of contraception for those participating in clinical studies.

Typical use failure rates may differ from those when used consistently and correctly. Use should be consistent with local regulations regarding the use of contraceptive methods for participants in clinical studies.

15. A woman of childbearing potential must have a negative urine pregnancy test at screening and at Week 0.
16. A woman must agree not to donate eggs (ova, oocytes) for the purposes of assisted reproduction during the study and for 12 weeks after the last dose of study intervention.
17. Criterion modified per Amendment 2.

17.1. Before randomization, a woman must be (as defined in Appendix 5 [Section 10.5], Contraceptive and Barrier Guidance and Collection of Pregnancy Information):

- a. Not of childbearing potential

OR

- b. Of childbearing potential and:

- If heterosexually active, practicing a highly effective method of contraception (failure rate of <1% per year when used consistently and correctly) and agrees to remain on a highly effective method while receiving study intervention and until 12 weeks after last dose (ie, the end of relevant systemic exposure). Examples of highly effective methods of contraception are located in Appendix 5 (Section 10.5), Contraceptive and Barrier Guidance and Collection of Pregnancy Information; however, the method selected must meet local/regional regulations/guidelines for highly effective contraception.
- If using oral hormonal contraceptives for birth control and receiving MMF/MPA, a woman must, in addition to the oral hormonal contraceptive, utilize a barrier method of birth control (eg, either an occlusive cap [diaphragm or cervical/vault caps] plus spermicidal

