9.4.6. Safety Analyses

All safety analyses will be analyzed using the SAS population (refer to Section 9.3 for definition).

Adverse Events

The verbatim terms used in the eCRF by investigators to identify AEs will be coded using the Medical Dictionary for Regulatory Activities. Any AE occurring at or after the initial administration of study intervention is considered to be treatment-emergent. All reported treatment-emergent AEs will be included in the analysis. For each AE, the percentage of participants who experience at least 1 occurrence of the given event will be summarized by intervention group. In addition, comparisons between intervention groups will be provided if appropriate.

The following analyses of AEs will be used to assess the safety of participants:

- Frequency and type of AEs.
- Frequency and type of SAEs.
- Frequency and type of reasonably related AEs as assessed by the investigator.
- Frequency and type of AEs leading to discontinuation of study intervention.
- Frequency and type of infections, serious infections, and infections requiring oral or parenteral antimicrobial treatment.
- Frequency and type of AEs temporally associated with an infusion.
- Frequency and type of injection-site reactions.

Summaries, listings, datasets, or participant narratives may be provided through Week 24 and Week 60 by treatment intervention, for the above AEs, deaths, and severe AEs. Selected safety summaries will also be performed for participants of the LTE (Section 9.4.8).

Clinical Laboratory Tests

Laboratory data will be summarized by type of laboratory test over time, and by treatment intervention. CTCAE toxicity grades (specified in the SAP) will be used in the summary of laboratory data. Descriptive statistics will be calculated for each laboratory analyte at baseline and for observed values and changes from baseline at each scheduled timepoint.

The following summaries of clinical laboratory tests will be used to assess participant safety:

- Laboratory parameters and change from baseline in laboratory parameters (hematology and chemistry).
- Summary of maximum CTCAE toxicity grade for postbaseline laboratory values (hematology and chemistry).

Listings of participants with any abnormal postbaseline laboratory values of CTCAE Grade ≥ 2 will also be provided.

Vital Signs

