5.7. Safety Analyses

Early Termination Note: Due to the Sponsor's decision to stop screening of new participants as a result of enrollment challenges, fewer than 60 participants will be enrolled in the study. The end of study will occur after all enrolled participants have completed the Week 20 visit or discontinued study intervention prior to Week 24, and all participants have completed their final efficacy and safety visits per the SoA.

For the CSR, all safety analyses described below will be performed on all available data through the end of study.

All safety analyses will be based on the safety analysis set based on actual intervention received, unless otherwise specified.

For all continuous safety variables, descriptive statistics by intervention group will include the N, mean, SD, median, minimum, and maximum. Categorical variables will be summarized by intervention group using frequency counts and percentages.

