5.7.2. Adverse Events

The verbatim terms used in the case report form by investigators to identify AEs will be coded using the Medical Dictionary for Regulatory Activities (MedDRA). Any AE occurring at or after the initial administration of study intervention is considered to be treatment emergent. If the event occurs on the day of the initial administration of study intervention, and either event time or time of administration are missing, then the event will be assumed to be treatment emergent. If the event date is recorded as partial or completely missing, then the event will be considered to be treatment emergent unless it is known to be prior to the first administration of study intervention based on partial onset date or resolution date. All reported treatment-emergent AEs will be included in the analysis. For each adverse event, the number and percentage of participants who experience at least 1 occurrence of the given event will be summarized by intervention group.

Summary tables and listings will be provided for treatment-emergent AEs:

- AEs
- Serious AEs (SAEs)
- AEs by severity, NCI-CTCAE toxicity grade
- AEs reasonably related to study intervention
- Had AEs leading to discontinuation of study intervention/termination of study participation

Summaries and listings of other treatment-emergent AEs of special interest will be provided. These include infections, serious infections, opportunistic infections, malignancies, hypersensitivity reactions, tuberculosis, AEs related to COVID-19, injection-site reactions, and AEs temporally associated with infusions.

Deaths will be displayed by actual study intervention received. A listing of study participants who died will be provided.

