5.7.3. Additional Safety Assessments**5.7.3.1. Clinical Laboratory Tests**

Clinical laboratory tests will be displayed for the participants included in the safety analysis set.

Descriptive statistics and graphical displays will be presented for selected chemistry and hematology, laboratory tests at scheduled time points.

Change from baseline through Week 24 and Week 52 will be summarized for chemistry and hematology tests and displayed by intervention group. A box plot of change from baseline through Week 24 and Week 52 will be provided.

- **Hematology assessments** will include but are not limited to the following: hemoglobin, hematocrit, platelet count, total and differential White Blood Cell count, B-cell analysis.
- **Blood chemistry assessments** will include but are not limited to the following: chemistry panel (total and direct bilirubin, alanine aminotransferase, aspartate aminotransferase, alkaline phosphatase, albumin, total protein, calcium, phosphate, sodium, potassium, chloride, blood urea nitrogen/urea, and creatinine).

The National Cancer Institute's Common Terminology Criteria for Adverse Events (NCI-CTCAE; version 5.0) will be used in the summary of laboratory data (Grade 0-4). The proportion of participants with post-baseline values by maximum toxicity grade for clinical laboratory tests will be summarized by study intervention group. Participants with toxicity grades ≥ 2 will be listed.

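### Treatment-emergent AEs and maximum laboratory grades have no cut-off tied to last dose or start of rescue, so events in early stoppers well after exposure ends count under the intervention received

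*Protocol*

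**What the plan says.** SAP 5.7.2 defines a treatment-emergent AE by its start alone: "Any AE occurring at or after the initial administration of study intervention is considered to be treatment emergent". Protocol 9.4.6 does the same. SAP 5.7.2 adds: "All reported treatment-emergent AEs will be included in the analysis". For laboratory data, SAP 5.7.3.1 states: "The proportion of participants with post-baseline values by maximum toxicity grade for clinical laboratory tests will be summarized by study intervention group". SAP 5.7 says that for the CSR "all safety analyses described below will be performed on all available data through the end of study", by intervention actually received.

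The limits that exist are calendar limits. AE collection ends with the last study-related procedure (Protocol 8.3.1). SAP 5.1 names Week 60. The early-termination text runs to end of study.

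Follow-up is set in Protocol 1.3, Table 1:
- Footnote c, permanent discontinuers who stay: "Participants who permanently discontinue study intervention, but do not withdraw from study participation, should be followed at all subsequent study visits through Week 60". If drug was stopped by Week 40, the Week 52 visit may serve as the final safety visit.
- Footnote c, participants on drug when sites are notified of termination: final safety visit about 12 weeks after last dose.
- Footnote d, those who stop drug and leave: a visit 12 weeks after last dose.

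Two further statements matter. Protocol 4.1.1 says: "Participants who experience an LN flare during the main study will be discontinued from study intervention", and defines a flare by the need for an immunomodulator change beyond what the protocol permits. Protocol 5.1, criterion 17.1, requires contraception "until 12 weeks after last dose (ie, the end of relevant systemic exposure").

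**The concern.** A participant who stops study drug early and stays in the study can contribute many weeks of AE and laboratory data after the protocol's own exposure window has closed. Where the stop was for a flare, that time may be spent on other immunosuppression. Infections and cytopenias arising then enter the same column as events on study drug.

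Stopping for flare is an outcome and may differ by arm. If more placebo participants stop, rescue-period events raise the placebo percentages and can dilute a true guselkumab excess. If more guselkumab participants stop, the reverse can happen. Serious infection is the first guselkumab risk listed in Protocol 2.3.1, and fewer than 60 participants will be enrolled.

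No planned AE or laboratory table separates these periods. SAP 5.7.1 counts participant-weeks from dosing days only, so no event rate over follow-up time is planned either.

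**Working it through.** **Follow-up arithmetic in the plan (Protocol 4.1.1 and 1.3).** 8 + 48 + 12 = 68 weeks in total, as stated. Last dose at Week 48 + 12 = Week 60, the final safety visit. Week 40 + 12 = Week 52, which matches the shortcut in footnote c. The schedule is thus built on last dose + 12 weeks; the AE and laboratory tables are not.

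**Time counted beyond last dose + 12 weeks**, for a stopper with last dose at week w who stays in the study:
- followed to Week 60: 60 − (w + 12) = 48 − w weeks, out of 60;
- followed to Week 52: 52 − (w + 12) = 40 − w weeks, out of 52.

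| Last dose (week) | Excess to Week 60 | Excess to Week 52 |
|---|---|---|
| 4 | 44 (73%) | 36 (69%) |
| 8 | 40 (67%) | 32 (62%) |
| 12 | 36 (60%) | 28 (54%) |
| 24 | 24 (40%) | 16 (31%) |
| 40 | 8 (13%) | 0 |
| 48 | 0 | not applicable |

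These are scheduled maxima for participants who stay.

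**Illustration of size.** The documents give no stopping or event rates, so all rates are assumptions: 20% of placebo and 5% of guselkumab participants have their last dose at Week 12 and stop for flare, and the serious-infection hazard h on rescue is 0.1 to 0.4 per year. Extra percentage in the placebo column from post-window time = (0.20 − 0.05) × [1 − exp(−h × t/52)].
- t = 36 weeks: h = 0.1, 0.2, 0.4 gives 1.0, 1.9, 3.6 points.
- t = 28 weeks: h = 0.1 and 0.4 gives 0.8 and 2.9 points.

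With the original 30 per arm, 1.0 to 3.6 points is 0.3 to 1.1 participants.

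**Dependence on unequal stopping.** Here the assumptions are more extreme: stoppers have last dose at Week 12 and stay to Week 60, and the 60-week risk on rescue is 50%. Hazards are −ln(1 − p)/60 per week. A stopper's risk is 1 − exp(−24 h_on − 36 h_rescue) over all follow-up and 1 − exp(−24 h_on) within last dose + 12 weeks.
- True on-drug 60-week risk 20% guselkumab, 10% placebo, 10% stopping in each arm: the difference is 9.3 points over all follow-up and 9.4 in the window. Almost no distortion.
- Same risks, 10% against 40% stopping: 22.0% against 20.7% (1.3 points) over all follow-up; 18.9% against 7.7% (11.2 points) in the window.
- Equal on-drug risk of 10%, 10% against 40% stopping: 12.7% against 20.7% over all follow-up (8.0 points lower on guselkumab); 9.4% against 7.7% in the window (1.8 points higher before rounding). Swapping the stopping rates reverses the signs.

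In the last case the first-event rate per person-time in the window is about 9.1 per 100 person-years in both arms. A windowed percentage alone therefore still carries unequal follow-up; a rate removes it in this model.

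**The case against.** The strongest reply is that counting all follow-up is a legitimate treatment-policy safety summary, safety is descriptive only, and in a trial this small the listings do the work. SAP 5.7.2 plans summaries and listings of SAEs, related AEs, AEs leading to discontinuation, infections and serious infections. SAP 5.7.3.1 lists grades 2 and above, SAP 5.2 lists discontinuers, and Protocol 9.4.6 allows narratives and a Week 24 summary. All of this stands as partial mitigation. It rests on investigator attribution or case-by-case reading, however, and gives no comparison by arm within an exposure window.

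The 12-week statement is a contraception criterion, not an AE attribution rule. That is correct. Still, the protocol uses the same 12 weeks for safety follow-up (4.1.1) and for classing deaths as SAEs (10.10.1), so it is the natural window to borrow.

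Readers might infer more than the documents support:
- *That events are collected without end, or charged to the randomised arm.* Collection ends at the final safety visit, and SAP 5.7 tabulates by intervention received.
- *That following discontinuers is the error.* It is good practice; only the tabulation lacks a cut.
- *That all participants are affected.* Those who leave, and those on drug at termination, are followed about 12 weeks after last dose and add no excess time.
- *That no safety item is limited to treatment.* SAP 5.7.3.3 restricts abnormal vital signs to the intervention period, without defining it.
- *That a few such events will decide the safety comparison.* No inferential safety test is planned in the SAP, and the first illustration amounts to about one participant or fewer.

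**Conclusion.** The point holds as a gap in tabulation. AE and maximum-grade summaries have no end relative to last dose or rescue, so post-exposure time in early discontinuers who stay is counted under the intervention they received. Early termination does not remove it: footnote c keeps the Week 60 rule for discontinuers, and SAP 5.7 keeps all safety analyses for the CSR.

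The excess time follows from the schedule: 36 of 60 weeks, or 28 of 52, for a last dose at Week 12. The effect on the comparison does not. It needs stopping, or off-drug risk, to differ between arms; its direction is open; and its size cannot be known from the documents. The range of 0.8 to 3.6 points depends wholly on the assumed 20% against 5% stopping and the assumed hazards. The larger swings come from deliberately extreme inputs and show only the mechanism. A conclusion that the plan will hide or create a safety signal would go beyond the evidence. This is a cheap improvement worth making.

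**What to change.** In SAP 5.7.2 and 5.7.3.1, keep the all-follow-up tables and add for the CSR, by intervention received:
- AEs, SAEs, infections, serious infections and maximum toxicity grade from first dose to last dose + 12 weeks;
- events after that window, shown separately;
- a flag for events after the start of rescue or prohibited therapy, since rescue may begin around drug stop and its first 12 weeks would otherwise sit unmarked inside the window;
- events per follow-up time for each window, because windowed percentages alone still reflect unequal follow-up.

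The dosing dates, AE records and concomitant therapy needed are already collected (Protocol 6.4, 6.5 and 8.3.1). The cost is SAP wording and one repeated table set, with no change to conduct. The downside is fewer events in the windowed tables.
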